8.3.10 Psoriatic Arthritis Screening and Evaluation (PASE)

The PASE questionnaire is a self-administered tool to screen for active PsA in subjects with PSO (Husni et al, 2014). The questionnaire consists of 15 items that are divided into a 7-item symptoms subscale and an 8-item functions subscale. Standardized responses are based on 5 categories relating to agreement (strongly agree [5], agree [4], no idea [3], disagree [2], and strongly disagree [1]). The total maximum score is 75 points (symptom score: 35 points and function score: 40 points). Psoriatic Arthritis Screening and Evaluation questionnaire scores ≥ 47 points are indicative of active PsA.

PASE will be collected at Baseline and Week 56/PEOT visit. PASE will be summarized based on OC only. No imputation is applied.

- Change from Baseline in the PASE questionnaire scores (function score, symptom score, and total score) is defined as Post-Baseline PASE questionnaire score (function, symptom, and total) minus Baseline PASE questionnaire score (function, symptom, and total).
- Shift from Baseline in PASE score suggestive of PsA (< 47 versus ≥ 47) is defined to Week 56/PEOT visit timepoint relative to Baseline.

8.3.11 Short Form – 36 Items Health Survey (SF-36)

The SF-36v2, standard recall, measures the following 8 health domains as rated by the subjects over the past four weeks: Physical Functioning, Role Physical, Bodily Pain, General Health, Vitality, Social Functioning, Role Emotional, and Mental Health (Maruish, 2011).

The SF-36 Physical and Mental Component Summary scores (PCS and MCS, respectively) are used to measure the two broad components, or aspects, of health-physical and mental. PCS and

MCS are based on the aggregate of 8 health concepts described above and all of the 8 health domain scales are used to score both components summary measures.

One additional item asks respondents about health change over the past year.

The SF-36 will be used using QualityMetric's Health Outcomes™ Scoring Software version 5.1 or later. The software uses updates 2009 U.S. population norms and applies a Full Missing Score Estimation (Full MSE) method as follows:

- A health domain score (except the physical functioning (PF) domain) will be estimated provided that at least one non-missing response is available within that domain
 - For the PF domain item response theory will be used to develop a model for estimates of the missing score (Thomas and Cyr, 2002)
 - Regression methods are then applied to estimate the PCS and the MCS on the basis of the available domains.
- Change from Baseline in Short Form 36-item Health Survey PCS score, and MCS score, and individual domains is defined as respective score at Post-Baseline timepoint minus the Baseline score.

8.3.12 Euro-Quality of Life 5-Dimensions, 3 levels (EQ-5D-3L)

The EQ-5D-3L health questionnaire provides a descriptive profile and a single index value for health status. The instrument is comprised of a 5-item health status measure and a visual analog scale (VAS).

Responses to EQ-5D-3L are scored as 1 for “no problem”, 2 for “some or moderate problems”, and 3 for “extreme problems”.

Absolute EQ-5D-3L VAS score records the respondent's self-rated health status on a vertical 20cm scale, 0 to 100 graduated (0=worst imaginable health status, 100=best imaginable health status).

Change from Baseline in EQ-5D-3L VAS scores is defined as Post-Baseline EQ-5D-3L VAS score minus Baseline EQ-5D-3L VAS score.

Responses to EQ-5D-3L will be summarized based on OC only as primary analysis. No imputation is applied to responses to EQ-5D-3L but is applied to EQ-5D-3L VAS scores.

8.3.13 Work Productivity and Activity Impairment Questionnaire – Specific Health Problem (WPAI-SHP)

The WPAI-SHP is a subject-reported questionnaire that assesses subject's employment status, work absenteeism, work impairment while working, overall work, and daily activity impairment attributable to a specific health problem. Five out of 6 items of the WPAI-SHP are regrouped into the 4 dimensions, with scores expressed as percentage, where higher numbers indicate greater impairment and less productivity, i.e., worse outcomes, as described in the WPAI-SHP scoring rules.

The scoring rules for the WPAI-SHP are as follows:

Questions:

- 1 = currently employed
- 2 = hours missed due to specified problem
- 3 = hours missed other reasons
- 4 = hours actually worked
- 5 = degree problem affected productivity while working
- 6 = degree problem affected regular activities

Scores:

- Percent work time missed due to problem: $[\text{Q2 hours}/(\text{Q2 hours} + \text{Q4 hours})] * 100$
- Percent impairment while working due to problem: $[\text{Q5 score}/10] * 100$
- Percent overall work impairment due to problem:
- $[\text{Q2 hours}/(\text{Q2 hours} + \text{Q4 hours}) + [(1 - (\text{Q2 hours}/(\text{Q2 hours} + \text{Q4 hours})) \times (\text{Q5 score}/10)]] * 100$
- Percent activity impairment due to problem: $[\text{Q6 score}/10] * 100$

Change from Baseline score is derived as post Baseline score minus Baseline score. A negative change score indicates a reduction in the score/improvement for the subject.

8.4 Additional statistical analysis of other efficacy variables

For selected efficacy variables, it is of interest to perform statistical tests and to calculate inferential statistics. As these tests are not part of the multiplicity-controlled procedure, the associated p-values are considered nominal and are not controlled for multiplicity.

For responder variables, the analysis will follow what was specified for the primary analysis. Specifically, a stratified Cochran-Mantel-Haenszel (CMH) test will be used, where region and prior biologic exposure (yes/no) will be stratification variables. The p-value will be based on the CMH test for a general association. Missing values will be imputed using NRI.

For continuous variables, the MI – MCMC / Monotone Regression approach used for other continuous variables will be applied for the imputation model. The analysis model will be based on analysis of covariance (ANCOVA) with fixed effects of treatment, region, and prior biologic exposure and Baseline value as a covariate.

Below is a list of variables for which these nominal p-values will be calculated (with the time points in parentheses). The results of these inferential tests will all be presented in a single table summarizing the testing performed outside of the multiplicity-controlled testing procedure.

- PASI90
 - Bimekizumab vs Adalimumab (Weeks 1, 3, 4, 8, and 12)
- IGA Clear or Almost Clear
 - Bimekizumab vs Adalimumab (Weeks 1, 3, 4, 8, and 12)

- PASI100
 - Bimekizumab vs Adalimumab (Weeks 4, 8, and 12)
- IGA Clear
 - Bimekizumab vs Adalimumab (Weeks 4, 8, 12, and 16)
- PASI75
 - Bimekizumab vs Adalimumab (Weeks 1, 3, and 16)
- PSD score - Pain
 - Bimekizumab vs Adalimumab (Week 16)
- PSD score - Itch
 - Bimekizumab vs Adalimumab (Week 16)
- PSD score - Scaling
 - Bimekizumab vs Adalimumab (Week 16)
- Scalp IGA Clear or Almost Clear (subjects with Baseline Scalp IGA ≥ 2)
 - Bimekizumab vs Adalimumab (Week 16)
- pp-IGA Clear or Almost Clear (subjects with Baseline pp-IGA ≥ 2)
 - Bimekizumab vs Adalimumab (Week 16)
- mNAPSI75 response (subjects with Baseline mNAPSI > 0)
 - Bimekizumab vs Adalimumab (Week 16)
- mNAPSI90 response (subjects with Baseline mNAPSI > 0)
 - Bimekizumab vs Adalimumab (Week 16)
- mNAPSI100 response (subjects with Baseline mNAPSI > 0)
 - Bimekizumab vs Adalimumab (Week 16)
- DLQI 0/1 response
 - Bimekizumab vs Adalimumab (Week 16)
- PASI percentage change from Baseline
 - Bimekizumab vs Adalimumab (Weeks 1, 3, 4, 8, 12, and 16)

9 PHARMACOKINETICS AND PHARMACODYNAMICS

9.1 Pharmacokinetics

Pharmacokinetic variables will be analyzed for all subjects in the PK-PPS. Bimekizumab plasma concentrations will be summarized for each treatment at each scheduled visit.

PK summaries will be based on observed values. No imputation will be used. However, if plasma concentration measurements are below the level of quantification (BLQ), then for

calculation of the derived statistics the result will be set to $\frac{1}{2}$ of the lower level of quantification (LLOQ). Descriptive statistics including geometric mean, geometric coefficient of variation, and geometric mean 95% CI if applicable will be calculated if at least $\frac{2}{3}$ of the values of interest are above the LLOQ. If this is not the case, only median, minimum, and maximum will be presented.

In addition, geometric mean plasma concentration will be plotted on a linear and log-linear scale by treatment group, and by cumulative antibody status for subjects randomized to bimekizumab.

If the dosing for a visit is ± 21 days out of window then the plasma concentration from that visit and all subsequent visits will be excluded from the PK summary.

If the PK sampling date is >1 day after the dosing date the data point will be excluded from the PK summary tables and figures.

However, all PK concentrations will be listed.

The PK will be subject to a population PK analysis, pooling data across phase 2 and 3 trials and will be described in a separate analysis plan and reported independently.

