5.6 Schedule of study assessments

The schedule of study assessments for all subjects enrolled in the study is presented in [Table 5–1](#). At each visit, all study assessments should be performed prior to administration of IMP.

Table 5–1: Schedule of study assessments

Visit ^a / Week	Screening	Double-blind Initial Treatment Period (weeks after first dose)										Dose-blind Maintenance Treatment Period (weeks after first dose)										W56/PEOT	SFU ^b		
		Baseline (first dose)	1	3	4	5, 7	8	9, 11	12	13, 15	16	17, 19	20	21, 23	24	28	32	36	40	44	48			52	56
Informed consent ^c	X																						X ^d		
Inclusion/exclusion	X	X																							
Urine drug screen	X																							X	
Demographic data	X																								
Psoriasis history	X																								
Significant past medical history and concomitant diseases	X	X ^e																							
Physical examination ^{f,g}	X	X							X					X			X			X			X	X	
Height		X																							
Body weight		X							X					X			X			X			X	X	
Vital signs ^h	X	X	X	X	X	X	X	X	X	X	X	X	X	X	X	X	X	X	X	X	X	X	X	X	X
Hematology and biochemistry	X	X	X	X	X	X	X	X	X	X	X	X	X	X	X	X	X	X	X	X	X	X	X	X	X
Urinalysis	X	X							X				X		X		X		X		X		X	X	
ECG	X							X					X			X			X		X		X		
Pregnancy testing ⁱ	X	X		X		X		X		X		X		X	X	X	X	X	X	X	X	X	X	X	X

Table 5–1: Schedule of study assessments

Visit ^a / Week	Screening	Double-blind Initial Treatment Period (weeks after first dose)										Dose-blind Maintenance Treatment Period (weeks after first dose)										W56/PEOT	SFU ^b			
		Baseline (first dose)	1	3	4	5, 7	8	9, 11	12	13, 15	16	17, 19	20	21, 23	24	28	32	36	40	44	48			52	56	
Hepatitis B and C testing ^j	X																									
HIV testing ^k	X																									
Chest x-ray ^l	X																									
IGRA Tuberculosis test	X																					X				
Tuberculosis questionnaire	X	X							X					X			X			X			X	X		
Blood sample for bimekizumab plasma concentrations ^m		X	X	X	X		X		X		X		X		X		X		X		X		X	X		
Blood sample for anti-bimekizumab antibodies ^m		X			X		X		X		X		X		X		X		X		X		X	X		
Blood sample genomic, proteomic, and metabolomics, and candidate biomarker analyses ^{c,m}		X	X				X		X		X													X		

Table 5–1: Schedule of study assessments

Visit ^a / Week	Screening	Double-blind Initial Treatment Period (weeks after first dose)										Dose-blind Maintenance Treatment Period (weeks after first dose)										W56/PEOT	SFU ^b			

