^j Subjects who have evidence of or test positive for hepatitis B by any of the following criteria: 1) positive for hepatitis B surface antigen (HBsAg+); 2) positive for anti-hepatitis B core antibody (HBcAb+) are excluded. A positive test for HCV is defined as: 1) positive for hepatitis C antibody (anti-HCV Ab), and 2) positive via a confirmatory test for HCV (for example, HCV polymerase chain reaction) are also excluded. Subjects will also be tested for anti-hepatitis B surface antibody.

^k The HIV test results will not be recorded in the eCRF.

^l Screening chest x-ray must occur within 3 months prior to Screening Visit.

^m All blood samples taken prior to dosing.

ⁿ The scalp IGA will only be assessed for those subjects with scalp involvement (scalp IGA score >0) at Baseline.

^o The mNAPSI will be assessed only in subjects with nail involvement (mNAPSI score >0) at Baseline.

^p The pp-IGA will only be assessed in subjects with palmoplantar involvement (pp-IGA score >0) at Baseline.

^q The Patient Global Assessment of psoriasis will be performed as part of the patient symptoms diary on a weekly basis from Screening through the Initial Treatment Period at the specified clinic visits. During the Maintenance Treatment Period this assessment will be completed at the specified clinic visits.

[figure not shown]
^r The PGADA is assessed for all subjects at Baseline. At all subsequent visits, the PGADA is only for subjects with PsA at Baseline (defined as a past medical history of PsA or PASE \geq 47).

^s IMP administration is based on randomization. The dosing window is \pm 3 days relative to the scheduled dosing visit through Week 24. The dosing window is \pm 7 days from Week 28 through the end of the study.

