10 ASSESSMENT OF PHARMACOKINETIC AND PHARMACOGENOMIC VARIABLE(S)

10.1 Pharmacokinetic variables

Blood samples for measurement of PK assessments ([Section 4.3.3](#)) will be collected at the time points specified in the schedule of study assessments ([Table 5–1](#)).

At dosing visits, blood samples will be drawn prior to dosing, and will be drawn at the same time of the sampling for clinical laboratory tests. The time and date of collection will be recorded in the eCRF.

Instructions pertaining to sample collection, processing, storage, labeling, and shipping are provided in the laboratory manual for this study. Detailed information on sample analysis will be provided in a bioanalytical report.

Pharmacokinetic samples from subjects receiving adalimumab will not be analyzed, but stored for potential future PK analysis and anti-drug antibody determination.

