3.2 Definition of Baseline values

A Baseline value for a subject is defined as the latest measurement for that subject up to and including the day of administration of first study medication, unless otherwise stated. If a Baseline assessment is taken on the same day as first administration of study medication, it is eligible to be used as the Baseline value, even in the case that the time of the assessment is recorded as taking place after the time of first study medication administration. This is considered acceptable as this measurement is still the best representation of the Baseline value of the given assessment since it is highly unlikely that the study medication could have an impact on any measurement in such a short period of time. However, such cases should be rare as study center personnel are instructed to do all assessments at the Baseline visit prior to administering study medication. One exception to this rule is plasma concentration. If Baseline plasma concentration is measured at a time after the first administration of study medication, then it should not be eligible to be considered as a Baseline plasma concentration. Such cases should be discussed with the quantitative clinical pharmacologist. If a Baseline measurement is missing or not collected, and a Screening value is available, the Screening value will be utilized as Baseline instead.

For subjects who start with adalimumab and switch treatment at the Week 24 Visit, an additional bimekizumab Baseline defined as the measurement at Week 24 will be used. If a Week 24 Visit measurement is missing, baseline will be the latest measurement prior to the first dose of bimekizumab. The variables listed below will also be summarized based on bimekizumab Baseline:

- PASI score

- DLQI
- Laboratory data (only in shift tables)

Note that for any laboratory value that occurs on the day of treatment switch, that lab value will be attributed and summarized for the treatment they were on previously. For subjects that switch from Adalimumab to Bimekizumab, the Baseline value is the laboratory value of the day of treatment switch.

Baseline values for component scores should be computed using components from the same visit where the relevant measurements were recorded prior to dosing. For example, if the Screening visit has all of the components, but the Baseline visit is missing one or more components, the Baseline value for the component score should be calculated using the Screening visit values.

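### The SAP's date-only PK exclusion rule would keep samples drawn after that visit's injection on the same or next day and summarize them with pre-dose values

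*SAP*

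**What the plan says.** SAP section 9.1 fixes how concentrations are reported: "Bimekizumab plasma concentrations will be summarized for each treatment at each scheduled visit". Its filter for late samples is "If the PK sampling date is >1 day after the dosing date the data point will be excluded from the PK summary tables and figures". The filter compares calendar dates and does not use clock time.

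The protocol sets the sampling time in three places. Section 10.1: "At dosing visits, blood samples will be drawn prior to dosing". Footnote m of Table 5-1, attached to the row for bimekizumab plasma concentrations: "All blood samples taken prior to dosing". Section 5.6, for procedures generally: "At each visit, all study assessments should be performed prior to administration of IMP". For sample timing, section 10.1 adds: "The time and date of collection will be recorded in the eCRF".

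SAP section 3.2 accepts same-day post-dose assessments as Baseline in general but makes an exception for plasma concentration. A Baseline concentration measured after the first administration is ruled out: "then it should not be eligible to be considered as a Baseline plasma concentration". No matching rule exists for later visits.

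**The concern.** At dosing visits the planned measurement is the level just before the next injection. A sample taken after an active injection measures something else, namely the residual level plus whatever part of the new dose has already been absorbed. Under the SAP rule both kinds of value would sit under the same visit label.

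Two displays could be misread. One is the table and plot of geometric mean concentration by treatment group, where the Q4W and Q4W/Q8W regimens are set side by side. The other is the plot by cumulative antibody status. A given late sample distorts the Q4W/Q8W arm more at its active-dose maintenance visits, because the pre-dose level there is lower.

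The SAP recognizes this problem for concentrations, since section 3.2 carves out the Baseline exception, but section 9.1 does not carry it forward.

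**Working it through.** The documents give no figure that depends on this rule, so there is nothing to reproduce. The check has two parts: what the rule keeps, and how far a kept late sample would be off.

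**What the rule keeps.** Let d be the sampling date minus the dosing date, in days.

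- d = 0, drawn before injection: kept, as intended.
- d = 0, drawn after injection: kept, contrary to the protocol's sampling time.
- d = 1: kept, contrary to the protocol's sampling time.
- d = 2 or more: excluded.

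**Where the injection is active.** Protocol section 7.2 and Table 7-1 give the injections, and the visit lists in section 8 give the post-Baseline PK samples (Weeks 1, 3, 4, 8, 12, 16, 20, 24, 36, 48, 56 and SFU). In both bimekizumab arms the injection is active at Weeks 4, 8, 12, 16, 24 and 48. At Weeks 20 and 36 it is active only in the Q4W arm. At Weeks 1 and 3 it is placebo in both arms. In the adalimumab/bimekizumab arm the question arises from Week 36, if those data are summarized. Week 56 and SFU have no study injection.

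**Size per sample.** Inputs:

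- Half-life 28 days (protocol section 2.2.1.1 reports 27.81 days sc and 28.25 days iv), so ke = ln 2 / 28 = 0.02476 per day.
- Absorption rate ka is not in the documents. It is assumed to be 0.1 to 1.0 per day.
- One compartment, linear, first-order absorption, dosing weeks from Table 7-1.

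For one dose at time 0, in relative units: C(t) = ka / (ka − ke) × [exp(−ke·t) − exp(−ka·t)].

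Pre-dose level P = sum of C over earlier doses. Next-day level L = the same sum one day later, plus C(1) from the new dose. Excess = L / P − 1.

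Example, Week 4, ka = 0.2: P = C(28) = 0.5664; C(29) = 0.5532; C(1) = 0.1790. Excess = (0.5532 + 0.1790) / 0.5664 − 1 = 29%.

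| ka per day | Q4W, Week 4 | Q4W, Week 48 | Q4W/Q8W, Week 48 |
|---|---|---|---|
| 0.1 | +15% | +6% | +19% |
| 0.2 | +29% | +13% | +44% |
| 0.5 | +71% | +35% | +108% |
| 1.0 | +119% | +58% | +179% |

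These are net figures: the one-day decline of the earlier doses is subtracted. The same formula at 1 to 2 hours after injection gives about 1% to 15% at Week 4 and under 8% at Week 48 in the Q4W arm. After a placebo injection (Q4W/Q8W, Week 20) the next-day value is about 2% lower, not higher.

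**Effect on a visit's geometric mean.** If a fraction f of samples is inflated by a factor r, the geometric mean is multiplied by r^f. With r from 1.15 to 2.0:

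- f = 1%: +0.1% to +0.7%
- f = 5%: +0.7% to +3.5%
- f = 10%: +1.4% to +7.2%

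The values of f are illustrative; the documents give no count of late samples.

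**The case against.** The strongest reply is that nothing goes wrong unless sites depart from an instruction the protocol gives repeatedly. If late samples are rare, a visit's geometric mean hardly moves. This stands, and a reader should not infer that post-injection levels will enter the summaries. The rule permits them; the documents do not show that they occur.

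A second reply is that PK summaries use the PK-PPS, defined to leave out important protocol deviations that would affect the concentration. This stands in part. The deviation criteria sit in a separate document, and neither the protocol nor the SAP names post-dose sampling as such a deviation. The set may catch some cases, but the SAP does not ensure that it does.

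A reader might also take the rule to delete every Week 56 and SFU sample, since these follow the last dose by weeks. The text does not support that. The preceding rule in SAP section 9.1 concerns the dosing for a visit, so the dosing date is naturally read as that same visit's date, and these two visits have none. Clearer wording would settle it.

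Two further inferences go too far. Not every late sample is inflated, because many injections are placebo. Nor can it be said that the geometric CV would rise: that was not calculated, and raising values that happened to be low could reduce the spread.

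**Conclusion.** The concern holds as a gap in the rule. SAP section 9.1 would keep same-day post-injection and next-day samples as that visit's concentration, against the protocol's sampling time and without the protection section 3.2 gives at Baseline. At active-injection visits the error in a single next-day sample could be material, and larger at Week 48 in the Q4W/Q8W arm than in the Q4W arm. The direction holds across the whole assumed absorption range, but the size depends on that assumption and on a one-compartment model.

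The effect on any reported summary is unknown, because the number of such samples is unknown. The matter is minor: no primary, secondary or multiplicity-controlled result is touched. Population PK and exposure-response analyses have their own plans, and all concentrations are listed in any case.

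**What to change.** Replace the rule in SAP section 9.1 with wording to this effect:

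- At visits where bimekizumab is injected, exclude from the PK summary tables and figures any sample whose recorded date and time is after that visit's injection.
- If a clock time is missing, exclude samples dated after the dosing date.
- Apply the rule only to that visit's own dosing date, so that it plainly does not reach Week 56 or SFU.
- Keep all values in the listings.

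If the one-day allowance was deliberate, state the reason and add a summary restricted to confirmed pre-dose samples.

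The cost is a wording change and a few data points moving from tables to listings. There is one dependency. Sample time is collected, but the rule also needs the injection time. Protocol section 7.2 says only that administration information is recorded in source documents, and SAP section 3.2 implies a recorded time for the first dose. Confirm that a time is captured for every dose before finalizing the rule.
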